3. STUDY DESIGN

The study is a randomized, response-adaptive, duration (dose) finding, comparative effectiveness clinical trial with blinded outcome assessment. The ideal range of durations to explore is unknown. Only in newborns with birth asphyxia associated hypoxic ischemic encephalopathy (HIE) have long durations been assessed. In this population, 72 hours was demonstrated to be superior to 96 hours duration of cooling. For adults and children, the longest duration of cooling reported in trials has been 48 hours. Because of this duration uncertainty, the P-ICECAP trial design, like the ICECAP trial, explores a broad range of durations. The design of this trial is based on a statistical model of the primary endpoint, the VABS-3 Mortality Composite Score, across the treatment arms. This is the duration-response model and all conclusions about the treatment arms are based on this model. The duration-response model is flexible and able to fit many different shapes for the duration-response curve. Specifically, it is parameterized to identify up to two change-points in the treatment effect across arms, allowing it to fit an increasing, decreasing, flat, plateau, or U-shape duration-response curve. The fit of the model is updated frequently with the emerging trial data and is used to adaptively randomize participants across the (up to) 10 treatment arms. The adaptive randomization algorithm effectively searches for the durations that provide the optimal treatment effect while also allocating participants to learn overall about the shape of the duration response curve.

Studies of the efficacy of therapeutic hypothermia in adults with OHCA used short durations of cooling. Cooling was maintained for 12 hours in one trial and for 24 hours in the two other trials. In newborns with birth asphyxia associated HIE, 72 hours is the standard of practice cooling duration. For the pediatric population, only one moderately large multicenter trial has been conducted. A duration of 48 hours was investigated which was midway between the adult 24 hours and neonatal 72 hours. For P-ICECAP, the study design will initially allocate participants to only the durations of 24 hours (the usual adult duration), 48 hours (the pediatric duration reported as safe as controlled normothermia) and 72 hours (the current standard neonatal HIE duration). As the trial continues, if the data suggest increasing efficacy with increasing duration, then the study design incrementally allocates to longer durations of cooling (up to 96 hours). Alternatively, if the data does not indicate increasing efficacy with increasing duration (or suggests an inverse relationship), the study design weights randomization toward shorter durations of cooling, including no additional cooling (controlled normothermia). This design minimizes the possibility of participants being allocated to durations of cooling that are too risky by virtue of being too short or too long and allows the study to consider a broad range of durations of cooling that would not otherwise be considered in a trial requiring fixed allocations to all treatment arms. There will be frequent interim analyses to stop the trial early for futility if no treatment arm offers a larger treatment benefit than the 0-hour duration arm.

3.1 Clinical Sites

At all participating sites, the usual clinical practice during the course of P-ICECAP for comatose pediatric OHCA survivors will be rapid initiation of TTM to a target within the local temperature range on arrival in the

[figure not shown]
pediatric intensive care unit (PICU); any definitive servo-regulated surface temperature control device may be used. Approximately 70 percent were former sites in the THAPCA trials. Approximately 45 hospitals are anticipated to each enroll an average of 4 participants per year. The enrollment period is anticipated to be 5 years (estimated accrual rate of 15 participants per month).

3.2 Randomization and allocation

Central computerized randomization by web-based interface will be used. Participants will be potentially randomized over the course of the trial to the following possible durations of cooling (in h): 0, 12, 18, 24, 36, 48, 60, 72, 84 and 96. The first 150 participants will be randomized 1:1:1 to the 24, 48, and 72-hour durations only. After this initial “burn in” period, response adaptive randomization will be used to allocate participants to other durations if the emerging duration-response curve (DRC) suggests that the largest treatment benefit might be on those durations. Randomization probabilities will be updated about every 10 weeks. At an expected accrual rate of 15 participants per month, 37 (range 30-45) interim participants would be projected. The 3-month VABS-3 Mortality Composite Score will be used in longitudinal modeling for adaptive randomization until the 12-month value is obtained. We have previously reported the 3- and 12-month VABS-II to be highly correlated ($r=0.95$) in the THAPCA trials (Slomine, 2019).

After the burn in period, the trial can open all arms. Allocation procedures are described in greater detail in Section 9 and in the Statistical Design appendix. Arms where the model proposes less than 5% allocation will be temporarily set to zero until the next interim look.

All of the possible durations that will be tested from 0 to 96 h are shown in the white shapes on the left in figure. The sequential columns of red circles represent randomization vectors as the trial progresses and participants accrue in the trial. After the burn-in period, shorter, longer, and interspersed arms may receive some allocation depending on the shape of the emerging DRC. The blue arrows at the top indicate automated “looks” at the data about every 10 weeks. At each look, there is a test for efficacy and futility and then calculation of the new randomization vector.

3.3 Blinding / masking

The primary outcome assessment in this trial will always be performed centrally by a study team member at the Kennedy-Krieger Institute (KKI), who is blinded to treatment as done in the THAPCA-OH trial. Participants themselves will be comatose during the intervention period. It is not practicable to blind the clinical care team or the participant's family to the duration of cooling. Study procedures to prevent inadvertent unblinding of the KKI include minimized contact between study team members involved in the study intervention and those performing follow up at 3 and 12 months through the use of centralized outcomes assessment. Participants and their family members will be instructed not to communicate any knowledge of the treatment group to the person assessing outcomes at any follow up visit. In addition, trial clinical leadership, as well as research teams, will be blinded to the outcome distribution by treatment arm, as well as to the updated allocation probabilities.

4. SELECTION AND ENROLLMENT OF PARTICIPANTS

Comatose pediatric survivors of OHCA who have already had initiation of a definitive temperature control device (e.g. Arctic Sun, Blanketrol III, etc.) will be considered for enrollment.

At all participating sites, the usual clinical practice during the course of P-ICECAP for comatose pediatric OHCA survivors will be TTM to targets of 33-37 °C on arrival in the PICU; any definitive servo-regulated surface temperature control device may be used. Families of patients who meet inclusion criteria will be approached for enrollment; cases with any initial presenting cardiac rhythm are eligible.

The inclusion and exclusion criteria detailed below stem both from actual clinical trial experience gained in the THAPCA-OH trial and modifications incorporated to broaden the scope of the P-ICECAP trial population (Moler, 2015).

4.1 Inclusion Criteria and Rationale

Inclusion Criteria

- Age 2 days to < 18 years with corrected gestational age of at least 38 weeks
- Chest compressions for at least 2 minutes
- Coma or encephalopathy after resuscitation from OHCA
- Requires mechanical ventilation through endotracheal tube or tracheostomy
- Definitive temperature control device initiated
- Randomization within 6 hours of ROSC
- Informed consent from LAR including intent to maintain life support for 120 hours*

Rationale for selected eligibility criteria - Inclusions:

Age

Age 2 days to <18 years with corrected gestational age of at least 38 weeks, incorporates the age group excluded from the adult ICECAP trial. The efficacy of different durations of therapeutic hypothermia in pediatric patients surviving cardiac arrest is unknown and is to be studied in this P-ICECAP trial. Brain recovery and outcome from cardiac arrest in children is markedly different from adults and likely represents a distinct medical condition. Furthermore, outcome markers used in the adult ICECAP trial are not validated or readily interpretable in young children.

Chest compressions for at least 2 minutes with coma or encephalopathy

Chest compressions for a minimum of 2 minutes combined with coma or encephalopathy indicate significant injury following pediatric OHCA. This was an inclusion criterion in the THAPCA-OH trial and identified a population with high mortality and high morbidity with approximately 13% found to have good outcomes within 1 standard deviation of baseline at 12 months post cardiac arrest (Moler 2015). The in-hospital pediatric population is excluded from P-ICECAP because there was no trend seen in the THAPCA-IH trial for benefit with cooling compared to normothermia. Additionally, this population has many comorbidities which are difficult to adjust for while pediatric OHCA is largely from a group that has normal baseline function.

Patient requires mechanical ventilation with a stable airway

For safety reasons, all post OHCA patients who are cooled require mechanical ventilation via a stable airway (endotracheal tube or tracheostomy) since deep sedation with or without neuromuscular blockade is commonly required for induction and maintenance of cooling to decrease shivering.

Definitive temperature control device applied

Inclusion requires that a definitive temperature control system be applied to ensure that participants are maintained at the target temperature for the allocated duration. Without such systems temperature lability is common and potentially dangerous in the range less than 32°C, but especially less than 30°C. Inability to maintain the target range would result in unplanned crossovers that add unnecessary variability and may dilute treatment effect. See 5.1.2 for the definition of definitive device.

Randomization within 6 hours of ROSC.

All participants will be randomized within 6 hours of ROSC and after the initiation of targeted temperature management. Enrollment is defined as the time of randomization.

Informed consent from a legally authorized representative (LAR) including intent to maintain life support for 120 hours.

Patients (comatose children) in this study meeting eligibility criteria are, by definition, unable to consent for themselves. The time window for the intervention in this study (randomized allocation to the duration of cooling, i.e., when rewarming will be initiated), however, makes it practicable to contact and engage in a consent process for enough eligible participants. Therefore, consent must be obtained from an LAR

(usually a child's parent) to enroll a pediatric patient in the study. LARs are also the surrogate decision makers in clinical practice regarding choices related to the timing of withdrawal of life support in the days following resuscitation. In the pediatric population unlike in adults, parents generally do not withdraw life support early, but wait many days to make end of life decisions. Nonetheless, the timing of withdrawal of life support is potentially a major confounder in the evaluation of duration of cooling after cardiac arrest. To reduce variability from this issue, the timing of potential withdrawal of life support under relevant scenarios must be discussed prior to enrollment. The principles guiding the timing of withdrawal of life-sustaining care for participants on the P-ICECAP protocol are intended to minimize bias by allowing each participant a similar exposure to the intervention, and a similar duration of intensive care and opportunity to awaken. Implementation of these principles will be detailed in the trial's clinical standardization guidelines. Only those patients whose LAR intend to maintain life support for 120 hours are to be enrolled.

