4.3 Study Enrollment Procedures

The on-call P-ICECAP study team will respond to the PICU clinical team’s notification to screen survivors of OHCA for eligibility, engage eligible patient’s LAR in an informed consent process, coordinate with the clinical care team, and randomize eligible participants. Enrollment case report forms will be completed in the PICU, where the study teams will determine and identify the sources for the times of arrest. Of note, this is routine information obtained by transport teams, pediatric emergency medicine specialists, and pediatric intensivists who care for children after OHCA.

The study team will follow each enrolled participant daily until day 10 for data collection and shepherding of clinical standardization through ICU stay. There is additional data collection at hospital discharge, and the follow up assessments at 3 and 12 months. P-ICECAP will use strategies described in THAPCA-OH that achieved a 98% one-year follow-up success rate (Gildea, 2020).

A screen log that includes all patients with a PICU diagnosis consistent with OHCA (ICD-10 code of I-46, I-46.2, I-46.8, I-46.9, I-49.01, I47.2, R95, R96, R98, R99, or equivalent codes in another diagnostic system) that are treated in the PICU but not enrolled will be completed at all sites.

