5. STUDY INTERVENTIONS

5.1 Interventions, Administration, and Duration

The intervention will be random allocation to duration of cooling after cardiac arrest, inclusive of a duration of no additional cooling (controlled normothermia) where the participant is set to a normothermic target after randomization. Cooling in the study will be by a definitive temperature control method to a target temperature of 33°C. Any FDA cleared surface temperature control device with closed loop feedback (servo regulated) will be allowed. Duration of cooling will be measured from the time that cooling is started as indicated by activation of a definitive cooling device (see 5.2 for definition) set to a target of 33°C (targets from 32- 34°C and maintained continuously prior to randomization also qualify as start of cooling). Sites are required to set the target temperature to 33°C within 15 minutes of randomization. Sites are required to have participant temperature below 34°C within 120 minutes of randomization. The constant practice seen in the THAPCA-OH trial was that 70% of pediatric OHCA cases were transported directly from outside community hospitals directly to the Pediatric ICU of the study site. For the remaining 30% of cases coming directly to the study site emergency department, the pediatric patients were resuscitated and if ROSC was achieved, these patients were transferred promptly to the PICU. On arrival to the PICU, arterial and central venous access were rapidly established, and targeted temperature management was initiated. In P-ICECAP, after the allocated duration of cooling is completed, controlled rewarming will be performed. Slow rewarming to a temperature of 36.8°C will occur over approximately 16 hours for those participants assigned to cooling durations greater than zero. After rewarming, a normothermic target will be used until 120 hours from device being set to the hypothermic target (see figure in section 4.3 above).

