5.4 Clinical Standardization

A clinical standardization guideline will be followed to reduce the effects of practice variability subsequent to randomization. Key physiologic and practice variables will be tracked and compliance with clinical standardization and deviation from physiologic targets reported back to study teams. Clinical standardization guidelines will include but may not be limited to the following: avoiding hypotension, avoiding hypoxia, treatment of seizures, management of sedation and paralysis, and defining and treating infections. Additional parts of clinical standardization may include monitoring of chemistries, CBC, coagulation tests and blood gases. Clinical standardization guidelines state that neurologic prognostication leading to withdrawal of life support is only allowed after 120 hours. The exception is when a participant meets the full brain death criteria at the clinical site. Recently, guidelines for post resuscitation management have been published by an expert international multidisciplinary group (Topjian, 2019, e194).

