7.1 Adverse Event Recording

All non-serious AEs occurring through 120 hours from setting the temperature control device to the assigned target and all serious adverse events (SAEs) occurring until participation in study has ended are recorded on the AE case report form (CRF) through the WebDCU™. The Site PI or Study Coordinator or designee is responsible for entering any and all AEs and SAEs into the database as soon as he/she becomes aware of the event and updating the information (e.g., date of resolution, action taken) in a timely manner. All non-serious AEs occurring through 120 hours must be recorded on the electronic AE CRF within 5 days from the time it was discovered by the site study personnel. For SAEs, the data entry must take place within 24 hours of discovery of the event. The NCI Common Terminology Criteria for Adverse Events (CTCAE) (see MoP) will be used to define severity of events.

The Site PI is responsible for the monitoring and follow-up of AEs until resolution or establishment of a new baseline and appropriate documentation in the participant research record. In addition to performing protocol-specified follow up, the participating PI must review all previously reported ongoing AEs to evaluate the current status. Upon completion of the study protocol by the participant, premature withdrawal from the study by the participant, or participant's death, all information regarding each AE must be completed, if not done so earlier.

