9.3 Statistical Models

9.3.1 Duration-Response Curve Model

We model the mean 12-month VABS-3 Mortality Composite Score across the ten treatment arms with a duration-response model. All conclusions about each treatment arm will be based on a duration-response model. The duration response model restricts the shape of the duration response curve to have 3 phases – an increasing phase, a plateau phase, and a decreasing phase. We create a parametric family for this inverted-U duration response model.

Let Y_i be the primary composite outcome measured at 12 months for the i^{th} participant. We model the outcomes as

$$Y_i \sim N(\theta_{d_i}, \sigma^2)$$

where θ_d is the mean response for arm d .

The U-shaped dose-response model allows for an initial increase in the mean with dose, followed by a leveling out of the mean, then a decrease. The dose-response curve can be characterized in four different regions of the dose space:

$$\theta_0 = \begin{cases} \theta_0 + \delta \left(\frac{d}{p_{min}} \right)^\alpha & 0 < d < p_{min} \\ \theta_0 + \delta & p_{min} < d < p_{min} + p_{width} \\ \theta_0 + \delta \left(1 - \frac{d - (p_{min} + p_{width})}{w_{width}} \right)^\beta & p_{min} + p_{width} < d < p_{min} + p_{width} + w_{width} \\ \theta_0 & d > p_{min} + p_{width} + w_{width} \end{cases}$$

where d corresponds to the duration of cooling index (1 through 10). For the lowest dose region near 0 hours ($d = 1$), the dose-response curve is modeled as (potentially) increasing. The next region is the plateau, where the dose-response curve is assumed constant. For the third region, the dose-response curve is decreasing. For the final region, the dose-response curve is again constant, at the same level as the zero-dose. Since some participants will be cool prior to randomization, the controlled normothermia arm is considered to be longer than zero in the above equation.

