In the null scenario where there is no difference in mortality nor in VABS-3 among the survivors across any duration of cooling, we control our Type I error rate at 5% as evidenced by the 4.6% shown in the “Power” column. We are able to (correctly) declare early futility in 24.6% of the trials in the null scenario. The controlled normothermia arm is the ED95 for the null case; 95.7% of trials correctly chose either controlled normothermia or the 12-hour duration as the ED95.

In our hypothesized effect size scenario used for the primary power calculations (bolded in the table above), where cooling benefit plateaus at 72 hours (“Plateau at 72 hours”), efficacy (a cooling duration is found to be associated with better outcomes on the VABS-3 Mortality Composite Score compared to the controlled normothermia arm, based on either the early stopping for success or final evaluation criteria as detailed above) is demonstrated in 92.3% of trials. We note that in this scenario, a small percentage of simulations (3.8%) stop early due to overwhelming evidence (at least a 95% probability) that the 96-hour duration was the cooling duration with maximum effect. This finding would usually be considered a “clinically acceptable” efficacy determination, as the 96-hour dose in fact has an effect equal to the 72-hour dose. In this scenario, we have excellent power to detect duration response, and we are not frequently choosing the 96-hour duration mid-trial when the 72-hour duration performs similarly. In this scenario, we correctly identify the ED95 window (i.e. 60 hours, 72 hours, 84 hours) 76.1% of the time. Considering a “within two durations” window (i.e., 48 hours through 96 hours), we identified an acceptable ED95 in 85.4% of the trials in our primary scenario.

We maintain approximately 90% power or more in all presented scenarios assuming efficacy of longer cooling durations under different true models, except when the duration of cooling has a U-shaped response for the VABS-3 Mortality Composite Score. In this (unexpected) scenario where better outcomes are associated with mid-range durations of cooling, but then drops at the longest durations, power is limited to 66.5% to declare that any duration of cooling is associated with better outcomes than controlled normothermia, and ability to correctly choose ED95 is also limited.

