11.1 Institutional Review Board (IRB) Review and Informed Consent

A single Central Institutional Review Board (CIRB) will be used for P-ICECAP pursuant to NIH policy for multicenter clinical trials. For sites outside the United States, an appropriate independent ethics committee will review and approve the protocol. The SIREN Emergency Research CIRB will be the IRB of record for all US sites. IRB approval for this trial must be obtained and maintained for all participating enrollment sites. Documentation of current IRB approval and other required IRB communications will be maintained within the WebDCU™ clinical trial management system.

Eligible participants in this trial will not have the capacity to provide informed consent. An informed consent process including written documentation from a legally authorized representative (LAR) (usually a parent) will be required. The process may be augmented by multimedia informational tools and an e-consent platform created for the study. Any tools or materials must be approved by the CIRB. In the absence of brain death or particularly malignant prognostic findings, it is consistent with common clinical practice to await signs of neurological improvement in comatose survivors of cardiac arrest over a period of 120 hours of life support if that is consistent with the wishes of a participant's family or LAR. An important element of the informed consent process will be to identify and only include participants for whom the family or LAR initially intend to pursue at least 120 hours of life support.

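### Does a common 120-hour floor on withdrawal of life support give the longer-cooled arms less opportunity to awaken?

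*Protocol*

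**What the plan says.** Section 4.1 calls the timing of withdrawal potentially a major confounder. It describes the governing principles as "intended to minimize bias by allowing each participant a similar exposure to the intervention, and a similar duration of intensive care and opportunity to awaken", and the next sentence leaves their implementation to the trial's clinical standardization guidelines. It also says that parents of these children generally wait many days before end-of-life decisions.

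Section 5.4 reports one rule from those guidelines: "neurologic prognostication leading to withdrawal of life support is only allowed after 120 hours", with full brain death criteria as the exception. No time zero is attached to it.

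Section 5.1 measures cooling from activation of the device at the hypothermic target. For arms above zero hours, "Slow rewarming to a temperature of 36.8°C will occur over approximately 16 hours", and a normothermic target then runs to 120 hours from the hypothermic setting. Section 7.1 records non-serious adverse events through "120 hours from setting the temperature control device to the assigned target".

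Section 11.1 describes it as common practice to "await signs of neurological improvement in comatose survivors of cardiac arrest over a period of 120 hours of life support".

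**The concern.** A single floor cannot hold both total support and post-rewarming time constant when cooling lasts from 12 to 96 hours. Each extra hour of cooling removes an hour of rewarmed observation before prognosis-based withdrawal becomes permissible. Section 4.1 also notes that deep sedation is commonly needed during cooling, so an hour cooled and an hour rewarmed may not be equal chances to wake.

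The care team and family know the arm (section 3.3), and death scores 0 on the primary outcome (section 6.1). If clinicians prognosticated at a fixed 120 hours, children in long arms might be judged sooner after rewarming and withdrawn more often. The duration-response model has a region that would absorb such deaths as lost benefit; in section 9.3.1, "For the third region, the dose-response curve is decreasing". The same scores drive adaptive allocation, so a distortion could also affect which arms are opened.

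**Working it through.** The protocol states no rewarmed time by arm, so there is no figure to reproduce.

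**Inputs.** Floor 120 h (section 5.4). Rewarming about 16 h (section 5.1). Randomization within 6 h of ROSC (section 4.1). Target set to 33°C within 15 minutes of randomization (section 5.1). Qualifying cooling may start before randomization (section 5.1).

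**Formula.** Minimum rewarmed time = 120 − cooling duration − 16, if the floor and the cooling clock share an origin. That shared origin is an assumption. If the floor runs from ROSC, cooling can start up to 6 + 0.25 = 6.25 h later. If it runs from randomization, cooling can start up to 6 h earlier or 0.25 h later.

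| Arm (h) | Floor from start of cooling | Floor from ROSC | Floor from randomization |
|---|---|---|---|
| 12 | 92 | 85.75 to 92 | 91.75 to 98 |
| 24 | 80 | 73.75 to 80 | 79.75 to 86 |
| 48 | 56 | 49.75 to 56 | 55.75 to 62 |
| 72 | 32 | 25.75 to 32 | 31.75 to 38 |
| 84 | 20 | 13.75 to 20 | 19.75 to 26 |
| 96 | 8 | 1.75 to 8 | 7.75 to 14 |

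For a given offset, the gap between the 24- and 72-hour arms is 80 − 32 = 48 h under any origin. The arithmetic behind the concern is right.

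**What the floor does deliver.** The sentence in section 4.1 names three properties. The first is similar exposure to the intervention. The longest arm finishes rewarming at 96 + 16 = 112 h, before the floor. With a ROSC clock and the latest start, 120 − 96 − 16 − 6.25 = 1.75 h remain. Only if rewarming also ran to an assumed 18 h would the margin vanish (−0.25 h). The second property, similar intensive care, is met at its minimum by a common floor. The third is met if it means time on support.

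**Scale of a possible bias.** The protocol gives no withdrawal rate by arm. At assumed survivor scores of 20 to 40 (20 is the VABS-3 minimum), the hypothesized 60-to-72-hour step of 41.3 − 39.3 = 2.0 points equals 2.0/40 = 5% to 2.0/20 = 10% of an arm. A fall like that at 96 h in the U-shaped scenario, 41.3 − 29.3 = 12.0 points, would need 12/40 = 30% to 12/20 = 60% of the arm moved to death by withdrawal alone, which is unlikely.

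**Would a sensitivity fit help?** Suppose deaths after prognosis-based withdrawal were rescored as low-scoring survivors. In the hypothesized scenario the means are 0.49 × 69 = 33.81 at 24 h and 0.55 × 75 = 41.25 at 72 h, a difference of 7.44. Take 80% of deaths as affected. This is an upper bound: it is the share section 6.2 gives for brain death or severe neurologic injury in the earlier pediatric trial, and brain death is exempt from the floor.

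- Score 20: 33.81 + 0.8 × 0.51 × 20 = 41.97; 41.25 + 0.8 × 0.45 × 20 = 48.45; difference 6.48.
- Score 40: 33.81 + 0.8 × 0.51 × 40 = 50.13; 41.25 + 0.8 × 0.45 × 40 = 55.65; difference 5.52.

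With no bias at all, the fit shrinks a true difference. It also cannot separate biased withdrawal from real harm.

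**The case for a change.** The strongest case for a change is that the protocol itself names withdrawal timing as a major confounder, and the undefined phrase is its stated control. Time zero and the meaning of a bias control are protocol matters. Section 11.1 describes usual practice and defines nothing. The imbalance follows the randomized factor exactly, in an unblinded trial with death in the endpoint.

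Part of this stands. The protocol text does not define opportunity to awaken, and section 5.4 gives no origin for its 120 hours. But sections 4.1, 5.1, 5.4 and 11.1 do not contradict one another: all use 120 hours, and no section adopts the post-rewarming reading on which the defect depends. The 120-hour consent criterion carries an asterisk whose footnote is not in the available text, and the figure cited in section 5.1 is not shown. Either could give the origin, as could the guidelines.

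On data capture, section 4.3 says: "The study team will follow each enrolled participant daily until day 10 for data collection". Collection also continues at hospital discharge, and serious adverse events are recorded until participation ends (sections 4.3, 6.4 and 7.1). None of these expressly lists the time and reason of withdrawal, but they give analysts most of what a descriptive comparison by arm would need.

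The protocol's U-shaped scenario, where "power is limited to 66.5% to declare that any duration of cooling is associated with better outcomes than controlled normothermia", is no evidence here. It simulates a true fall in benefit, not withdrawal practice.

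**Conclusion.** No change to the plan follows. Minimum time after rewarming does differ by arm: 80, 56 and 32 hours in the three initial arms and 8 hours at 96 hours, assuming about 16 hours of rewarming and a floor counted from the start of cooling. Another origin moves these levels by about 6 hours at most. But the common floor holds minimum total support similar and leaves room for the planned cooling and rewarming in every arm. That is a fair trade-off, because no single floor can equalize both quantities.

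The hours are minimums, and section 4.1 expects families to wait longer. A bias against long arms is plausible but unmeasured and probably small. Defining the phrase and stating time zero would only write down detail that the guidelines, the footnote or the figure may already contain. Withdrawal timing by arm can be described from data largely being collected. The rescoring analysis would cut a true 7.4-point difference to as little as 5.5 without resolving the question. This conclusion takes opportunity to awaken to mean time on support, the reading section 11.1 favours. Which clinical rule applies is for the sponsor.
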